Appendix

Executive Summary

Patient safety is a cornerstone for providing excellent healthcare. A fall will result in increased cost for the patient as well as the facility due to increased hospital stay and treatments. Most falls that occur within acute care settings are preventable and fall prevention is the key to reducing falls that will result in injuries and increased expenses. “For adult patients in the hospital (P) how does hourly rounding (I) compared to no hourly rounding (C), affect incidence of falls (O) during the patient’s stay? This PICOT question was formulated to attain evidence through scholarly literature research that proves that purposeful hourly rounding can help reduce inpatient falls. Hourly rounding is a process already utilized on most acute care units. My project involves using the PDSA method to implement a revised hourly rounding process with aim to decrease the fall rate. Costs associated with this improvement project are minimal but the benefits of reducing injury and costs associated with a fall, are vast. This project involves educating staff on the revised rounding process, implementing the new process over a three-month time, and comparing fall data from three months prior to the project’s implementation to data from the three-month implementation time period to evaluate the effect that purposeful hourly rounding can have on fall reduction. Fall rate comparisons, video monitoring, chart audits, and patient surveys will prove that the new rounding protocol has been implemented and provide evidence of the benefits that rounding can have on patient safety.

Rationale

Every year anywhere from 700,000 to 1,000, 000 falls will occur for inpatients. Injuries will result from 30-35% of these inpatient falls. A typical fall can cost around 14,000 in increased treatment cost and extended hospital stay costs. In fact, in 2013, inpatient falls for older patients cost the US Healthcare system \$34 billion, (MarketScale, 2020). Many of these costs, related to an inpatient fall, will not be reimbursed by Medicare. One source, (PSNet, 2019), states that falls happen at a rate of 3 to 5 per 1000 bed days. Falls can result in severe injury and even death. According to the CDC, in 2018, approximately 54 out of 100,000 patients in Texas die because of a fall, and falls are the leading cause of injury related deaths among patients aged 65 and older (CDC). Injuries that result from a fall not only may require expensive treatments, and lengthen the hospital stay but they also decrease patient confidence. Patients may lose confidence in their mobility and become more sedentary because of fear of falling again. Measures can be taken to prevent a fall. Many patients fall while trying to do a simple task, unaccompanied, such as going to the restroom or trying to find a possession such as a cellphone. Hourly rounding includes assessing the patient's environment, addressing any needs they have, making sure the call light is within reach, and the bed alarm is activated. These simple tasks can have a large impact on fall prevention. While hourly rounding is already utilized on most nursing units, this project includes a more in-depth rounding process and required documentation in the patient's electronic chart. Through literature research, evidence has been accumulated that proves that purposeful hourly rounding will help to increase patient safety and reduce costs associated with a fall.

Literature Synthesis

Research was conducted using eleven scholarly articles that used hourly rounding as a fall prevention tool. The articles chosen for appraisal showed a decrease in the fall rate post intervention implementation. One article, (Hicks, 2015), was a literature review that summarized fourteen study findings related to hourly rounding used as a fall prevention intervention. In all fourteen studies investigated in this article, only one showed an increase in the fall rate after hourly rounding, and two showed no change. Eleven of the study findings incorporated in the fourteen-study article, highlighted a decrease in fall rate after implementing hourly rounding. Of the other ten articles that were critically appraised, eight had a dramatic decrease in the fall rate after hourly rounding was implemented. Only two articles did not find a significant decrease in the fall rate post implementation of the hourly rounding process. Kuwaiti & Subbarayalu, 2017, found a dramatic drop in the fall rate after adding an hourly rounding process from 6.57 to 1.91. Another article found that the number of falls decreased from 442 to 247 as well as an 81% reduction in costs associated with falls after adding hourly rounding, (Jenko, M., Panjwani, Y., & Buck, H., 2019). Spano-Szekely et al, 2019 also found a 54% reduction in the fall rate and a savings of \$84,000 in costs associated with falls after using an hourly rounding process. Through deep research using scholarly articles that detailed study finding related to using hourly rounding as a fall prevention tool, many article findings resulted in a reduction in the fall rate as well as money saved from fall related costs. This evidence proves that incorporate a realigned rounding process to patient care will have a beneficial impact for the acute care unit and healthcare facility.

Stakeholders

Stakeholders of this project include administration, the education team, nurses and other caregivers, and the patients. Administration will give approval for the project, make assessments regarding data attained from the projects implementation, create documentation that will be incorporated in the patient's chart, create patient surveys regarding the rounding interactions, and set policies for how hourly rounding will be utilized in other areas of the facility. The education team will be incorporated in educating staff during, staff meetings, on the new rounding procedures, and role-model staff interactions with patients during these rounds. The patients are stakeholders for this project as well. This project is centered around fall prevention and increasing patient safety. Patients will be interacting with staff during the rounds and will also be asked to complete a survey about the hourly rounds.

Implementation

Hourly rounding is an intervention that has potential to decrease the fall rate. This is a quality improvement project plan to implement structured hourly rounding process using the Plan, Do, Study, and Act method.

Plan Stage – 2 weeks

Research conducted has proven that many facilities have implemented hourly rounding that has proven effective for fall prevention. Purposeful hourly rounding involves checking on patients, at regular intervals to assess and address the patient's pain level, body positioning, proximity to possessions, bathroom needs, and peacefulness of environment. During these rounds, staff are to also identify potential fall hazard, patient's access to the call light, and usage of bed rails/bed

alarms. During this planning stage, evidence from research of scholarly articles will be shared with administrators and other stakeholders. Following the projects approval, unit administrators, safety committee members, and staff educators will develop training and education that addresses the need for this intervention, how the process works, required documentation, and accountability measures connected to the project's implementation. Staff will observe role modeling of required hourly rounding interactions. This training will take place during required staff meetings.

Do Stage – 12 weeks

After staff education about purposeful, hourly rounds and all expectations connected to the process, the intervention will be implemented over a twelve-week time. The rounds are to be completed hourly from 0700 to 2200 and every two hours from 2300 to 0600. During the rounds, staff are to assess the patient's pain, bathroom needs, proximity to possessions, body positioning, and peacefulness of their environment. Staff will also assess and monitor for trip hazards, closeness of the call light, and use of bed rails/bed alarm. These rounds will be documented, after completion, in the patient's electronic medical record. Patients will be given a survey to fill out on the day of discharge, about the rounding experiences.

Study Stage – 1 week

During this stage, the fall rate from twelve weeks prior to implementation of the hourly rounding process will be compared to the fall rate for the twelve-week implementation time. Any fall that occurs during this time must be analyzed using root cause analysis to determine if it was accidental or intentional. An audit of video monitoring and chart audits of hourly rounding

documentation will be used to evaluate if hourly rounding had been completed, as expected. Feedback scores from patient surveys will be compiled and evaluated.

Act Stage- 1 week

After evidence of the effect that hourly rounding has on fall reduction, this process will be adopted as policy. New rounding policy and procedure will be adopted, and the process will be extended to and shared with other units within the facility.

Timetable/Flowchart

PLAN Phase – 2 weeks - Project evidence shared with stakeholders; project education completed

DO Phase – 12 weeks – Hourly rounding implemented, patient surveys on rounding sent to patients to be completed and returned

STUDY Phase – 1 week – Fall rates for pre and post implementation period is compared, video monitoring completed, chart audits of rounding documentation

ACT Phase – 1 week- Data shared with administration, new rounding policy adopted, rounding procedure policy expanded to other units

Data Collection Methods

The center of quality improvement is the planned effort to test a change decipher its result on a desired outcome. One widely utilized method for testing and learning about a change and its desired outcome is the PDSA or, plan, do, study, and act, method, (Melnik & Fineout-Overholt, 2019). This method will be used to implement my change project. After the “DO” phase, the

information gained will be analyzed and evaluated in the “STUDY” phase. Evaluation is an integral part of quality improvement projects and critical information can be gleaned from careful evaluation. Evaluation is useful for several different reasons including monitoring the impact of local projects, identifying, and dealing with issues as they arise within a project, comparing local projects to draw lessons, and collecting more detailed information as part of a bigger evaluation project, (Harvey & Wensing, 2003). To evaluate the effect that purposeful hourly rounding has on the fall rate, data from pre and post implementation will be compared. The fall rate for twelve weeks prior to the new rounding processes will be determined per 1,000 patient days. This number will be compared to the fall rate per 1,000 patient days during the twelve-week study period. These numbers will be compared to determine if a decrease in the fall rate happened after the change was implemented, using a chi-square test of independence to determine statistical significance. Chart audits to evaluate documentation of the hourly rounds as well as video monitoring of staff entrance/exit into patient rooms, will be evaluated. Patients will also be surveyed on the frequency and content of these staff rounds. Outcome information gathered will be shared with all stakeholders. Administrators will make decisions about adopting the new rounding policy and extending the policy and procedure to other units.

Cost/Benefit Discussion

The safety benefits that this project has far outweighs the costs associated is implementing this project. Costs associated with this project include time devoted to training development with staff educators. Another cost associated with the project includes money need to add a rounding documentation component to patient charts. Additional costs include printing the patient surveys

needed to obtain patient feedback concerning the hourly rounds. Overall costs for this project should be minimal compared to the benefits of decreased falls and increased patient safety. Additional benefits include money saved from injury related costs that are unreimbursed through Medicare.

Overall Discussion/Results

Recommendations

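### As written, the 12-week baseline runs up to the start of the new rounding and so takes in the 2-week Plan stage, when staff are trained; early uptake could modestly dilute the effect

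*Protocol*

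**What the plan says.** Two operative sections of the protocol set the comparison window, and both tie it to the start of the new rounding.

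- Data Collection Methods: "The fall rate for twelve weeks prior to the new rounding processes will be determined per 1,000 patient days".
- Implementation, Study Stage: the same anchor in other words. The reference rate comes from the twelve weeks before rounding is put in place, and it is set against the rate in the twelve weeks of the Do stage.

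The rounds start in the Do stage, once staff education is done. What comes just before is in the Timetable/Flowchart: "PLAN Phase – 2 weeks - Project evidence shared with stakeholders; project education completed". The Plan Stage text adds what staff see in that time: "Staff will observe role modeling of required hourly rounding interactions. This training will take place during required staff meetings".

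The Executive Summary describes the window more loosely: "comparing fall data from three months prior to the project’s implementation to data from the three-month implementation time period".

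No section gives calendar dates, a washout, or an exclusion of the Plan weeks.

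**The concern.** This is an uncontrolled before-after comparison, so the baseline carries the whole contrast. It should represent the unit before staff were exposed to the project. The intervention is staff behaviour, and the Executive Summary says that hourly rounding is already used on most acute care units. A nurse who has been trained could therefore change how patients are checked without waiting for the official start.

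If that happens inside the baseline, the reference fall rate is lower than true usual care and the measured reduction shrinks. Administrators will use this comparison when they decide whether to adopt the rounding policy and extend it to other units. A real benefit would become slightly harder to see in a short study with few falls.

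**Working it through.** The protocol states no sample size, power or expected effect, so it has no figure of its own to reproduce. The check covers the overlap and the dilution that could follow.

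**Inputs from the protocol**
- Baseline 12 weeks, ending when the rounds start (Data Collection Methods; Study Stage).
- Plan stage 2 weeks, directly before the 12-week Do stage (Timetable/Flowchart).
- Effects taken from the protocol's own literature: 3.37 to 2.6 and 2.51 to 1.15 falls per 1,000 patient days (Evidence Synthesis Table), and 6.57 to 1.91 (Literature Synthesis).
- Background rate of 3 to 5 falls per 1,000 bed days (Rationale).

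**Assumed, not in the protocol**
- *w*: baseline weeks in which trained staff could act early (1 or 2).
- *f*: share of the full effect present in those weeks (0.5 or 1).
- A true rate ratio (RR) of 0.50 as a round illustration.
- Equal patient days per week.
- For precision and power: 1,680 to 5,040 patient days per period, and two-sided alpha 0.05.

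**Step 1: overlap.** 2/12 = 16.7%. The Plan Stage text puts sharing the evidence and approval first, then development of the training, then its delivery. Staff exposure is therefore shorter than two weeks. With one exposed week the share is 1/12 = 8.3%.

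**Step 2: dilution.** In the affected weeks the fall rate is the usual rate times 1 − f(1 − RR). Averaged over 12 weeks:

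observed RR = RR / [1 − (w/12) · f · (1 − RR)]

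For RR = 0.50:
- w = 2, f = 1: 0.50 / (1 − 0.0833) = 0.545
- w = 2, f = 0.5: 0.50 / (1 − 0.0417) = 0.522
- w = 1, f = 0.5: 0.50 / (1 − 0.0208) = 0.511

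For the literature effects, as percentage reductions with w = 2:

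| Rates | True | Observed, f = 1 | Observed, f = 0.5 |
|---|---|---|---|
| 3.37 to 2.6 | 22.8% | 19.8% | 21.4% |
| 2.51 to 1.15 | 54.2% | 49.6% | 52.0% |
| 6.57 to 1.91 | 70.9% | 67.0% | 69.1% |

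The largest shifts are 3.0, 4.6 and 3.9 percentage points.

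**Step 3: the shift against sampling error.** At RR 0.50 the upper-bound shift is ln(0.545/0.50) = 0.087 on the log scale. The standard error of the log rate ratio is √(1/falls before + 1/falls after).
- 1,680 patient days at 3 per 1,000: 5.04 and 2.52 falls, SE 0.77, so the shift is 11% of one standard error.
- 5,040 patient days at 5 per 1,000: 25.2 and 12.6 falls, SE about 0.35, so the shift is 25% of one standard error.

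**Step 4: power.** This uses a two-proportion approximation per patient day. With 2,520 patient days per period, 4 falls per 1,000 and a 54% reduction, power is 0.30 with a clean baseline, 0.26 at half effect in both weeks, and 0.23 at the upper bound. Over the whole assumed range of patient days and fall rates, the upper-bound loss is about 3 to 12 percentage points.

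**The case against.** The strongest reply is that overlap in the calendar is not exposure. The new rounds and their charting are described under the Do stage, the intervention is said to follow staff education, and no passage says that the rounds are delivered earlier. The full effect in both weeks would require every staff member to be trained on the first day and to change at once. This stands: one sixth is a ceiling, and the upper-bound figures are limits rather than expectations.

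A second reply is that no end date is fixed, and that the Executive Summary's phrase about the project's implementation could mean the start of the whole project, in which case there is no overlap. That ambiguity is real, but it does not override the two operative sections, which both name the start of the rounding.

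Three stronger readings are tempting and are not supported:
- A reader might infer that a sixth of the control period is contaminated. The sequence inside the Plan stage rules this out for the approval and development days, and early uptake afterwards is a possibility, not a stated fact.
- A reader might infer that training also raises fall reporting and so inflates the baseline. The listed training topics are the need for the intervention, the process, its documentation and accountability; fall reporting is not among them. Better reporting would also be expected to continue into the Do stage.
- A reader might infer that the protocol gives three conflicting windows. The operative sections agree on twelve weeks; the Executive Summary's three months is a second, looser description, plausibly rounding.

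**Conclusion.** The point holds as a minor one. On its plain wording the protocol's baseline includes up to 2 of 12 weeks of planning and training, with no exclusion. This is a window that the protocol itself states, not a detail it has left open.

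If trained staff act early, the fall reduction is understated by at most about 3 to 5 percentage points for the effects in the protocol's own literature, and probably by less. The direction is toward no difference, so early uptake by this route cannot manufacture a benefit. The size depends on the assumed uptake, which the protocol does not give. The overlap depends on the Plan stage running directly into the Do stage, as the timetable lists them.

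**What to change.** In Data Collection Methods and the Study Stage, define the baseline as the 84 days ending the day before the Plan stage begins. Exclude the two Plan weeks from both periods as a transition. Record the calendar dates of all three intervals, and replace three months in the Executive Summary with the same 12-week wording.

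The baseline keeps its length, so no information is lost. The drawback is that it lies two weeks further from the intervention period, which gives slightly more room for drift in case mix or season. The only other cost is changing the dates of a retrospective data pull.

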Appendix B

PICOT Question:

For adult patients in the hospital (P), how does hourly rounding (I) compared to no hourly rounding (C), affect incidence of falls (O) during the patient's hospital stay (T).

Evidence Synthesis Table

Studies	Design	Sample	Intervention	Outcome
A	Systematic literature review	Sample Size varied for each of the 14 studies evaluated	Rounding	
Brosey & March (2014) – FR decreased from 7.02 to 3.18/1,000 PD
 
Ciccu-Moore et al (2014) – FR decreased 39% during study period
 
Dupree et al (2014) – FR decreased from 4.001 to 2.613/1,000 PD
 
Fisher et al (2014) – FR decreased from 5.42 to 3.94/1,000 PD
 
Ford (2010) – No falls reported during the study
 
Kolin et al (2010)- FR decreased from 361 to 214
 
Krepper et al (2012) – FR on control and experimental units were similar
 
Kessler et al (2012) – FR decreased from 5.46 to 2.19/1,000 PD
 
Meade et al (2006) – 25 falls in four weeks prior to intervention, 12 falls during intervention period
 
Olrich et al (2011) – FR decreased from 3.37 to 2.6/1,000 PD, 23% decrease in falls
 
Saleh et al (2011). FR decreased from 25 falls to 4
 
Sherrod et al (2012) – FR slightly increased from 4.3 to 4.5

				Tucker et al (2012) – FR 4.5, 1.6, and 3.2, decreasing at first then increasing Woodward (2009)- FR decreased
B	Descriptive Study – pilot project	N=60	IR	-FR decreased 44% from 442 per 1,000 PD to 247 per 1,000 PD from the pre-implementation to post implementation time L/D P -There was an 81% reduction in replacement costs from pre-implementation and post-implementation time
C	Descriptive Study – clinical practice improvement project	N=245	FPP	-With implementation of the FPP, there was a 54% reduction in FR from 2.51 per 1,000 PD for 2014, to 1.15 FR per 1,000 PD for the last half of 2016 and the first half of 2017. -There was a 72% reduction in SU after the implementation of the FPP, that resulted in \$84,000 in savings.
D	Explanatory cross-sectional Study	N=2,170 RN surveys	RNV– including BS, NL, AL, MN,	BS – 4.10 EM (0.69 SD) NL- 4.03 EM (0.68 SD) AL – 4.06 EM (0.69 SD) MN – 3.88 EM (0.78 SD) PP – 4.07 EM (0.69 SD)
E	Retrospective Study- medical record review	N=140	FPP (including bed/chair alarms, hourly rounding, patient education)	FR decreased 0.6 falls per 1,000 PD

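### The chi-square test is specified on two fall rates per 1,000 patient-days with no table or unit of analysis defined; if the rates are entered as written, the p-value ignores the real patient-days

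*Protocol*

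**What the plan says.** The relevant text is in the protocol under Data Collection Methods. For the earlier period, "The fall rate for twelve weeks prior to the new rounding processes will be determined per 1,000 patient days". For the later period, "This number will be compared to the fall rate per 1,000 patient days during the twelve-week study period". The next sentence takes those two figures as its subject: "These numbers will be compared to determine if a decrease in the fall rate happened after the change was implemented", and the method is "using a chi-square test of independence to determine statistical significance".

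This is the only inferential test named in the protocol. No contingency table is described. The unit of analysis (patient, patient-day or fall) is not stated, and nothing is said about a patient who falls more than once. No number of beds or patient-days is given. Each period is twelve weeks; under Implementation, "the intervention will be implemented over a twelve-week time".

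**The concern.** A chi-square test of independence works on counts of independent units cross-classified in a table. A rate per 1,000 patient-days is not a count; it is a count divided by exposure and rescaled. Once rescaled, it no longer shows how many patient-days were observed, and the test needs that information.

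The sentence makes the two rates the thing compared, so an analyst who follows it literally would enter them as events out of 1,000. Another analyst could build a table of falls against fall-free patient-days, and a third could count fallers against non-fallers. These can give different p-values from the same data, and the protocol does not choose between them in advance. The evaluation informs the administrators' decision on adopting the rounding policy and extending it to other units, so the ambiguity affects the main conclusion.

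**Working it through.** **Inputs.** From the protocol: twelve weeks (84 days) per period; a cited background of 3 to 5 falls per 1,000 bed days (Rationale); a cited drop from 6.57 to 1.91 (Literature Synthesis, no unit given there, taken here as per 1,000 patient-days). Assumed, because the protocol gives no exposure: equal patient-days N in each period, with N = 2,142 (30 beds × 0.85 occupancy × 84 days), 5,040 (60 occupied beds × 84 days) or 10,000; a two-sided 5% level. The protocol states no sample size, power or p-value, so there is no figure of its own to reproduce.

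**1. Rates entered as counts out of 1,000.** With rates p1 and p2 and their mean p, the Pearson statistic without continuity correction is

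X² = (p1 − p2)² / [p(1 − p) × 2/N].

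For 4 versus 2 per 1,000 and N fixed at 1,000: X² = 0.002² / (0.003 × 0.997 × 0.002) = 0.67, p = 0.41, whatever the size of the unit. The expected fall count per cell is 3.0, below the usual minimum of 5.

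For the cited drop from 6.57 to 1.91: X² = 0.00466² / (0.00424 × 0.99576 × 0.002) = 2.57, p = 0.11. So one of the largest effects that the protocol cites would not reach 5% on this reading at any unit size.

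**2. The same rates with actual exposure.** X² is proportional to N, so the literal version equals the real one multiplied by 1,000/N. The Poisson score statistic is (p1 − p2)² / (p × 2/N).

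| Patient-days per period (assumed) | X² on falls vs fall-free days | p | Poisson score p |
|---|---|---|---|
| 2,142 | 0.6687 × 2.142 = 1.43 | 0.2314 | 0.2321 |
| 10,000 | 0.6687 × 10 = 6.69 | 0.0097 | 0.0098 |

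The literal reading gives 0.41 in both rows.

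**3. Error rate of the literal version.** With equal true rates of 3 to 5 per 1,000 (200,000 simulated Poisson replicates per setting), the type I error at a nominal 5% was 0.0067 to 0.0084 at 1,680 patient-days per period, 0.0013 to 0.0016 at 2,520, and about 0 at 10,080. The test is therefore conservative once exposure exceeds 1,000 patient-days, which is about 12 occupied beds (1,000/84 = 11.9). Below that the scaling works the other way.

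**4. A worked example.** Take 25 versus 12 falls on 5,040 patient-days each.
- Chi-square on falls and fall-free days: X² = 4.58, p = 0.032.
- Poisson score: (25 − 12)²/37 = 4.57, p = 0.033.
- Literal rates: 4.58 × 1,000/5,040 = 0.91, p = 0.34.
- Rate ratio: 12/25 = 0.48; standard error of its log √(1/25 + 1/12) = 0.351; 95% interval 0.24 to 0.96.

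**5. Repeat falls.** If repeat falls inflate the variance by a factor φ (assumed; the protocol has no data on this), a nominal 5% two-sided test has an actual level of 2[1 − Φ(1.96/√φ)]: 8.6% for φ = 1.3, 11.0% for 1.5 and 16.6% for 2.0. This applies equally to the chi-square on patient-days and to a plain Poisson test.

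**6. Fallers versus non-fallers.** The denominator becomes patients. Length of stay drops out and a second fall adds nothing, so the comparison is of a proportion of patients and not of the rate that the protocol defines.

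**The case against.** The strongest reply is that nobody can calculate a rate per 1,000 patient-days without the fall count and the patient-days, so a sensible analyst would use those. On that reading the chi-square test is sound in practice. At rates this low it is almost the Poisson score test: in every scenario tried the p-values differed by about 0.001 or less, and the simulated type I errors were nearly identical. This stands. A reader might infer that the planned p-value will be wrong whatever the analyst does; the protocol does not support that.

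Second, a reader might infer that the plan yields no effect size. It does not say so. Both rates are produced and compared, so a ratio or difference follows at once, and an interval may be left to a statistical analysis plan that is not shown. What remains is that the chi-square test on its own supplies no interval.

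Third, the non-directional test might be called an error because the question is about a decrease. Testing two-sided and reading the direction from the rates is ordinary practice.

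Fourth, the repeat-fall problem is not peculiar to chi-square. An exact or score Poisson test without a dispersion term has essentially the same inflation, so changing the name of the test would not cure it.

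The objection does not remove the text itself: the protocol makes the two rates the object of the test and defines no table. The literal reading is open, and it errs against detecting a benefit in any unit of more than about 12 occupied beds.

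**Conclusion.** The point holds as a moderate correction. The protocol attaches a test for counts to two rescaled rates and leaves the unit of analysis undefined. Followed literally, the p-value ignores exposure: 0.41 for 4 versus 2 per 1,000, against about 0.23 at 2,142 and 0.01 at 10,000 patient-days per period. With falls and fall-free patient-days in the table the p-value is close to that of a Poisson comparison, and the remaining weakness is the lack of any allowance for repeat falls. The exposures and variance-inflation factors are assumptions. The loss of exposure information on the literal reading does not depend on them, but its size and direction do.

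**What to change.** Replace the chi-square sentence in Data Collection Methods with wording such as: the number of falls in each twelve-week period will be compared by a rate ratio with actual patient-days as exposure. Both fall counts, both patient-day totals and the rate ratio with its 95% confidence interval will be reported. The standard error will be scaled for over-dispersion, using a quasi-Poisson model on weekly fall counts with a log patient-days offset. A sensitivity analysis will count only each patient's first fall.

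The cost is one paragraph and a little more analysis. Fall counts and patient-days are already needed for the rates; they must also be tabulated by week, and falls linked to patients. The interval may widen: in the worked example, φ = 1.5 raises the standard error from 0.351 to 0.351 × √1.5 = 0.430 and changes the interval from 0.24–0.96 to 0.21–1.12. Dispersion will be poorly estimated if falls are few: at 2,142 patient-days, 4 and 2 per 1,000 mean about 8.6 and 4.3 falls, or 0.7 and 0.4 per week over 24 weekly counts. The change does nothing about the uncontrolled before-and-after design, which is a separate matter.
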